#### **9.4.8. Other Tests**

Not applicable.

#### **9.4.9. Safety Monitoring**

Lilly will periodically review evolving aggregate safety data within the study by appropriate methods. Lilly will also review SAEs within the time frames mandated by company procedures. The Lilly CRP will, as appropriate, consult with the functionally independent Global Study participant Safety therapeutic area physician or clinical scientist.

##### **9.4.9.1. Hepatic Safety Monitoring**

If a study participant experiences elevated ALT  $\geq 3X$  ULN, ALP  $\geq 2X$  ULN, or elevated TBL  $\geq 2X$  ULN, liver testing ([Appendix 4](#)) should be repeated within 3 to 5 days including ALT, AST, ALP, TBL, direct bilirubin, gamma-glutamyl transferase (GGT), and creatine kinase to confirm the abnormality and to determine if it is increasing or decreasing. If the abnormality persists or worsens, clinical and laboratory monitoring should be initiated by the investigator and in consultation with the study medical monitor. Monitoring of ALT, AST, TBL, and ALP should continue until levels normalize or return to approximate baseline levels.

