Hypoglycemia events	X	X	X	X	X	X	X	X	X	X	X	X	X	X	X	X	X	X	X	X	X	X	X	X	X	X	X	X	
AE/SAE review			X	X	X	X	X	X	X	X	X	X	X	X	X	X	X	X	X	X	X	X	X	X	X	X	X	X	Will include injection site inspections
Laboratory Assessments																													
LY3209590 PK			X e	X	X	X	X	X	X	X	X				X		X				X		X	X	X	X	X	See Section 9.5	
Fasting		X	X			X			X						X		X				X	X		X	X	X	X		
Serum pregnancy test (WCBP only) a	X																											See Section 5.1 Central lab	

Procedure	Screening and Lead-in		Treatment Period																			Follow-up			ET	Notes a					
	1	2	3	4	5	6	7	8	9	10	11	12	13	14	15	16 b	17	18 b	19 b	20	21	22 b	801 c	802 c			803 c				
eCRF Visit Number	-2	-1	0	1	2	3	4	5	6	7	8	9	10	11	12	13	14	15	16 b	17	18 b	19 b	20	21	22 b	801 c	802 c	803 c			
Weeks																															
Visit window, days	±7	±3		±2	±2	±3	±2	±2	±3	±2	±2	±2	±2	±2	±3	±3	±3	±3	±3	±3	±3	±3	±3	±3	±3	±3					
Urine pregnancy test (WCBP only)			X																				X		X		X	X		Local lab	
Urinalysis	X																						X		X	X	X	X			
Chemistry panel a	X	X	X						X						X		X						X	X		X	X	X	X	Visit 2: glucose, AST, ALT, GGT only	
Pancreatic Amylase	X																														
Lipase	X																														
Hepatitis B	X																														
HbA1c	X		X						X						X		X						X	X			X		X		
Hematology	X		X						X						X		X						X	X		X	X	X	X		
FSH	X																													Female study participants only	
eGFR	X														X								X			X					
HDL, LDL		X	X												X								X		X	X	X	X			
Free fatty acid, triglycerides		X	X			X			X						X		X						X		X	X	X	X		Collected in fasting state	
C-peptide			X			X			X						X								X		X	X	X	X		Collected in fasting state	
LY3209590 anti-drug antibodies a		X					X			X					X								X		X	X	X	X		See Section 9.4.7	

Procedure	Screening and Lead-in		Treatment Period																			Follow-up			ET	Notes a
	1	2	3	4	5	6	7	8	9	10	11	12	13	14	15	16 b	17	18 b	19 b	20	21	22 b	801 c	802 c		
eCRF Visit Number	-2	-1	0	1	2	3	4	5	6	7	8	9	10	11	12	15	18	21	24	28	32	33	37			
Weeks	±7	±3		±2	±2	±3	±2	±2	±3	±2	±2	±2	±2	±2	±3	±3	±3	±3	±3	±3	±3	±3				
Pharmacogenetic sample			X																							

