## 8. Discontinuation Criteria

### 8.1. Discontinuation from Study Treatment

#### 8.1.1. *Permanent Discontinuation from Study Treatment*

Possible reasons leading to permanent discontinuation of IP:

- **Subject Decision**
  - the study participant or the study participant's designee, for example, parents or legal guardian requests to discontinue IP.
- **Discontinuation due to a hepatic event or liver test abnormality.**
  - Study participants who are discontinued from IP due to a hepatic event or liver test abnormality should have additional hepatic safety data collected via eCRF.

Discontinuation of the IP for abnormal liver tests **should be** considered by the investigator when a study participant meets one of the following conditions after consultation with the Lilly designated medical monitor:

- ALT or AST >8X ULN
- ALT or AST >5X ULN for more than 2 weeks
- ALT or AST >3X ULN and total bilirubin level (TBL) >2X ULN or international normalized ratio >1.5
- ALT or AST >3X ULN with the appearance of fatigue, nausea, vomiting, right upper-quadrant pain or tenderness, fever, rash, and/or eosinophilia (>5%)
- alkaline phosphatase (ALP) >3X ULN
- ALP >2.5X ULN and TBL >2X ULN
- ALP >2.5X ULN with the appearance of fatigue, nausea, vomiting, right quadrant pain or tenderness, fever, rash, and/or eosinophilia (>5%)

In addition, study participants will be discontinued from the IP in the following circumstances:

- if a study participant is inadvertently enrolled and it is determined that continued treatment with IP would not be medically appropriate (see Section 8.1.3)
- if a study participant is diagnosed with an active or untreated malignancy (other than basal or squamous cell skin cancer, in situ carcinomas of the cervix, or in situ prostate cancer) after randomization
- if a study participant is diagnosed by the investigator with acute or chronic pancreatitis
- if a study participant is diagnosed with C-cell hyperplasia or medullary thyroid carcinoma after randomization

- if the investigator or sponsor decides that the study participant should be withdrawn from IP; if the investigator decides to permanently discontinue IP because of an SAE or a clinically significant laboratory value, Lilly or its designee should be alerted immediately.

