## 9.2. Adverse Events

Investigators are responsible for monitoring the safety of study participants who have entered this study and for alerting Lilly or its designee to any event that seems unusual, even if the event may be considered an unanticipated benefit to the study participant.

The investigator is responsible for the appropriate medical care of study participants during the study.

Investigators must document their review of each laboratory safety report.

The investigator remains responsible for following, through an appropriate health care option, AEs that are serious or otherwise medically important, considered related to the IP or the study, or that caused the study participant to discontinue the IP before completing the study. The study participant should be followed until the event resolves, stabilizes with appropriate diagnostic evaluation, or is reasonably explained. The frequency of follow-up evaluations of the AE is left to the discretion of the investigator.

Lack of drug effect is not an AE in clinical studies, because the purpose of the clinical study is to establish treatment effect.

After the ICF is signed, study site personnel will record via eCRF the occurrence and nature of each study participant's preexisting conditions, including clinically significant signs and symptoms of the disease under treatment in the study. In addition, site personnel will record any change in the condition(s) and any new conditions as AEs. Investigators should record their assessment of the potential relatedness of each AE to protocol procedure, IP, via eCRF.

The investigator will interpret and document whether or not an AE has a reasonable possibility of being related to IP, study device, or a study procedure, taking into account the disease, concomitant treatment or pathologies.

A "reasonable possibility" means that there is a cause and effect relationship between the IP, study device and/or study procedure and the AE.

The investigator answers yes/no when making this assessment.

Planned surgeries and nonsurgical interventions should not be reported as AEs unless the underlying medical condition has worsened during the course of the study.

If a study participant's IP is discontinued as a result of an AE, study site personnel must report this to Lilly or its designee via eCRF, clarifying if possible, the circumstances leading to any dosage modifications, or discontinuations of treatment.

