#### **Hepatic Safety Data Collection**

Additional safety data should be collected via the eCRF if 1 or more of the following conditions occur:

- elevation of serum ALT to  $\geq 5X$  ULN on 2 or more consecutive blood tests
- elevated serum TBL to  $\geq 2X$  ULN (except for cases of known Gilbert's syndrome)
- elevation of serum ALP to  $\geq 2X$  ULN on 2 or more consecutive blood tests
- study participant discontinued from treatment due to a hepatic event or abnormality of liver tests
- hepatic event considered to be an SAE.

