- elevation of serum ALT to ≥ 3 -fold ULN on 2 or more consecutive blood tests
- elevation of serum ALT to ≥ 5 -fold ULN on 2 or more consecutive blood tests
- elevation of serum AST to ≥ 3 -fold ULN / 5-fold ULN on 2 or more consecutive blood tests
- elevated serum TBL to ≥ 2 -fold ULN (except for cases of known Gilbert's syndrome)
- elevation of serum ALP to ≥ 2 -fold ULN on 2 or more consecutive blood tests
- study participant discontinued from treatment due to a hepatic event or abnormality of liver tests
- hepatic event considered to be an SAE

will be provided, including the actual measurement of ALT, AST, TBL, ALP, and the corresponding reference of high limits.

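### An isolated AST rise does not trigger the 3-to-5-day repeat or entry into liver monitoring in Section 9.4.9.1, although AST alone can meet a stopping criterion in Section 8.1.1

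*Protocol*

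**What the plan says.** **Retest rule (Protocol 9.4.9.1).** The rule begins "If a study participant experiences elevated ALT". Its triggers are ALT ≥3X, ALP ≥2X and TBL ≥2X ULN. The first step is a repeat panel within 3 to 5 days, which includes AST and creatine kinase. If the abnormality persists or worsens, the investigator starts clinical and laboratory monitoring in consultation with the medical monitor. The last step reads "Monitoring of ALT, AST, TBL, and ALP should continue until levels normalize or return to approximate baseline levels".

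**Stopping criteria (Protocol 8.1.1).** Stopping study drug is to be considered, after consultation, on several grounds. One is "ALT or AST >5X ULN for more than 2 weeks". The other aminotransferase grounds also name ALT or AST: above 8X ULN, above 3X with raised TBL or INR, and above 3X with symptoms or eosinophilia.

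**Additional hepatic eCRF data (Protocol, Hepatic Safety Data Collection).** The only aminotransferase criterion starts "elevation of serum ALT to" and is set at 5X ULN or more on consecutive tests. AST has no counterpart.

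**SAP 4.10.4.2.** The elevation tables cover ALT and AST alike. The patient listing includes an item that starts "elevation of serum AST to", at 3-fold and 5-fold ULN on consecutive tests.

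**The concern.** A duration criterion needs at least two values. For ALT, Section 9.4.9.1 calls for an early second value and for monitoring if the rise persists. For AST alone, with ALT <3X, ALP <2X and TBL <2X ULN, nothing in either document calls for another value before the next scheduled chemistry. Yet the stopping list treats the two enzymes the same.

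Section 3.3 names aminotransferase elevation as an additional risk from preclinical data. It had not been seen in people, but their exposure was at most 6 weeks, and this trial treats for 32. At stake is whether a marked isolated AST rise is confirmed promptly and followed as a matter of procedure, or only if the investigator chooses to do so.

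**Working it through.** **1. Is AST covered anywhere?** Triggers in 9.4.9.1: ALT, ALP, TBL. Aminotransferase stopping grounds in 8.1.1: ALT or AST. AST is in the second set and not the first. The closing sentence of 9.4.9.1 names AST, but it is the end of a pathway that an isolated AST rise never enters.

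The other provisions set neither an AST threshold nor a retest time:
- Section 9.2: "Investigators must document their review of each laboratory safety report". It also makes the investigator follow medically important adverse events until they resolve, stabilize or are explained, at a frequency the investigator chooses.
- Section 9.4.6: a laboratory finding must be reported as an adverse event when it results in a diagnosis, so an asymptomatic AST rise may not become one.
- Section 9.4.9: "Lilly will periodically review evolving aggregate safety data within the study by appropriate methods". This is review at group level.
- Appendix 4: further hepatic tests are optional, or may be required after consultation with the sponsor.

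**2. Does the plan treat AST as a lesser liver marker?** Mostly not. AST above 2.5X ULN excludes at entry (criterion 16). Section 10.3.1 averages three baseline values for ALT, AST and GGT. The chemistry note in the Schedule of Activities reads "Visit 2: glucose, AST, ALT, GGT only". The stopping list and the SAP tables pair AST with ALT.

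**3. Time to the next required AST value.** In the chemistry row of the Schedule of Activities, post-baseline draws through Week 18 fall at Visits 9, 15 and 17 (Weeks 6, 12 and 18), each with a ±3-day window. The SAP's laboratory fasting glucose time points (Weeks 6, 12, 18 and 32) agree with this reading. Intervals after Week 18 are not used, because the table columns are displaced there in the available text.
- Nominal gap: 6 weeks × 7 = 42 days.
- With both windows: 42 − 6 = 36 to 42 + 6 = 48 days.
- Delay relative to an ALT-triggered repeat at 3 to 5 days: 36 − 5 = 31 to 48 − 3 = 45 days.

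Up to Week 12 there are weekly site visits at which a discretionary draw is easy. Between Weeks 12 and 18 the only scheduled contact is the Week 15 phone visit.

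**4. Who is affected?** For the 2-week criterion: AST above 5X and up to 8X ULN, with ALT, ALP and TBL below their triggers and no symptoms or eosinophilia. AST above 8X, or above 3X with raised TBL or with symptoms or eosinophilia, can be acted on without an AST-triggered repeat. The documents give no rate for the affected group.

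**The case against.** **ALT-led monitoring is coherent.** Section 10.3.4 names ALT as the liver biomarker among the safety measures, and some AST rises come from muscle. This stands as a possible motive. It does not explain why entry, baseline, stopping and analysis all use AST beside ALT, and no reason is given for leaving it out of the trigger.

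**Retesting is already implied.** An investigator told to judge an AST duration cannot do so without a second value, and Section 9.2 carries a general duty of follow-up. This stands, and it limits the harm. It supplies no threshold and no date, and it depends on the rise being treated as a medically important event.

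**The 2-week criterion is no better served for ALT.** A reader might subtract 14 from 36 to 48 days and infer that AST is judged 22 to 34 days late because of this omission. The documents do not support that. A repeat at 3 to 5 days does not settle a duration of more than 2 weeks, and 9.4.9.1 dates no later ALT draw, so a Day-14 value is not guaranteed for either enzyme. Those 22 to 34 days describe the chemistry schedule.

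**Reporting is barely affected.** A reader might infer that transient AST rises drop out of the results. They do not. SAP 4.10.4 lists every abnormal laboratory value in the safety population, and 4.10.4.2 tabulates any post-baseline AST elevation. AST-related discontinuations and hepatic SAEs also reach the hepatic eCRF. Without a discretionary retest, a rise that resolves before the next scheduled draw misses only the consecutive-test listing.

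**The SAP listing and the eCRF criteria need not match.** A reader might see their difference as an error. One lists laboratory values and the other prompts extra data collection, and they already differ for ALT: the listing starts at 3-fold, the eCRF criterion at 5X.

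**Conclusion.** The gap is real and narrow. As written, Section 9.4.9.1 gives an isolated AST rise neither the early confirmatory draw nor required entry into monitoring, both of which the same multiple of ULN in ALT would bring. Between Weeks 6 and 18 the next required AST value comes 36 to 48 days after the first, 31 to 45 days later than an ALT-triggered repeat. This assumes that visits keep to their windows and that no discretionary retest is done.

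The affected group is small, and its rate is not in the documents. Stopping under 8.1.1 is something to consider and is not automatic. The point concerns participant safety procedures and does not touch the efficacy analysis. It is worth correcting because the correction is cheap.

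**What to change.** 1. In Section 9.4.9.1, make the first trigger *ALT or AST ≥3X ULN*.
2. For consistency, add *or AST* after ALT in the first Hepatic Safety Data Collection criterion, keeping the 5X ULN consecutive-test rule. This aligns with the 5-fold tier of the SAP's AST listing only, not with its 3-fold tier.
3. Have the sponsor's medical team confirm both AST limits.

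**Cost.** Two wording changes and some extra draws. As an assumption with no support in the documents, suppose 0.5% to 2% of the 375 randomized participants have an isolated AST ≥3X ULN. That is 375 × 0.005 = 1.9 to 375 × 0.02 = 7.5, or about 2 to 8 people. With up to 3 draws each (also assumed), the upper end is 7.5 × 3 = 22.5, or about 23 draws. A 3-to-5-day repeat may need an added visit. Later draws can use the weekly site visits up to Week 12, but need an added visit between Weeks 12 and 18. Some repeats will follow AST of muscle origin, which the creatine kinase already in the repeat panel helps to identify.

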#### **Hepatic Safety Data Collection**

Additional safety data should be collected via the eCRF if 1 or more of the following conditions occur:

- elevation of serum ALT to  $\geq 5X$  ULN on 2 or more consecutive blood tests
- elevated serum TBL to  $\geq 2X$  ULN (except for cases of known Gilbert's syndrome)
- elevation of serum ALP to  $\geq 2X$  ULN on 2 or more consecutive blood tests
- study participant discontinued from treatment due to a hepatic event or abnormality of liver tests
- hepatic event considered to be an SAE.

## 9.5. Pharmacokinetics

At the visits and times specified in the Schedule of Activities (Section 2), venous blood samples will be collected to determine the plasma concentrations of LY3209590. After Visit 3, PK samples can be taken at any time during the visit.

Instructions for the collection and handling of blood samples will be provided by the sponsor. The actual date and time (24-hour clock time) of each sampling will be recorded.

All the samples will be analyzed at a laboratory by the Sponsor, and stored at a facility designated by the Sponsor.

Plasma concentrations of LY3209590 will utilize a validated enzyme-linked immunosorbent assay method.

Bioanalytical samples collected to measure IP concentration will be retained for a maximum of 1 year following last study participant visit for the study.

## 9.6. Pharmacodynamics

In addition to PD parameters already discussed in the efficacy and safety sections, fasting plasma free fatty acids and fasting triglycerides will be evaluated as PD biomarkers of lipolysis, which is a sensitive measure of peripheral insulin activity.

## 9.7. Pharmacogenomics

### 9.7.1. Whole Blood Samples for Pharmacogenetic Research

A whole blood sample will be collected for pharmacogenetic analysis as specified in the Schedule of Activities (Section 2) where local regulations allow.

All samples will be coded with the study participant number. These samples and any data generated can be linked back to the study participant only by the investigator site personnel.

Samples will be retained at a facility selected by Lilly or its designee for a maximum of 15 years after the last study participant visit for the study, or for a shorter period if local regulations and/or ERBs/investigational review boards impose shorter time limits. This retention period enables use of new technologies, response to regulatory questions, and investigation of variable response that may not be observed until later in the development of LY3209590 or after LY3209590 becomes commercially available.

Molecular technologies are expected to improve during the 15-year storage period and therefore cannot be specifically named. However, existing approaches include whole genome or exome sequencing, genome wide association studies, and candidate gene studies. Regardless of technology utilized, genotyping data generated will be used only for the specific research scope described in this section.

## 9.8. Biomarkers

Biomarker research is performed to address questions of relevance to drug disposition, target engagement, PD, mechanism of action, variability of study participant response (including safety), and clinical outcome. Sample collection is incorporated into clinical studies to enable examination of these questions through measurement of biomolecules including DNA, RNA, proteins, lipids, and other cellular elements.

Serum and plasma samples for non-pharmacogenetic biomarker research will be collected at the times specified in the Schedule of Activities (Section 2) where local regulations allow.

Samples will be used for research on the drug target, disease process, variable response to LY3209590 pathways associated with T2DM, mechanisms of action of LY3209590 and/or research methods, or in validating diagnostic tools or assay(s) related to T2DM.

All samples will be coded with the study participant number. These samples and any data generated can be linked back to the study participant only by the investigator site personnel.

Samples will be retained at a facility selected by Lilly or its designee for a maximum of 15 years after the last study participant visit for the study, or for a shorter period if local regulations and ERBs impose shorter time limits. This retention period enables use of new technologies, response to regulatory questions, and investigation of variable response that may not be observed until later in the development of LY3209590 or after LY3209590 become(s) commercially available.

## 9.9. Health Economics

No health economic outcomes are planned.

## 10. Statistical Considerations

### 10.1. Sample Size Determination

Approximately 375 study participants will be randomized in a 1:1:1 ratio to LY3209590 in one of two dosing algorithms or insulin degludec treatment arms, assuming a 20% dropout rate resulting in approximately 300 total completers at 32 weeks (100 completers per treatment arm). The sample size was calculated based on the statistical power for the primary and liver safety endpoints.

- The 300 completers will provide 90% statistical power to demonstrate the noninferiority of the pooled LY3209590 arms versus insulin degludec for the change in HbA1c from baseline to 32 weeks (assuming non-inferiority margin is 0.4%, the SD is 1.1% and true mean difference is 0%) using two sided t-test at  $\alpha = 0.1$ .

### 10.2. Analysis Sets

For purposes of analysis, the following populations and analysis sets are defined:

Population and Analysis Set	Description
Enrolled	All study participants who sign informed consent
All randomized study participants	All study participants who are randomly assigned a treatment arm
Efficacy analysis set (EAS)	Data for all randomized study participants who received at least one dose of study medication, excluding data after using rescue medication or stopping study medication (last dose date + xx days). In the event of a treatment error, participants will be analyzed according to the treatment they actually received.
Full analysis set (FAS)	Data for all randomized study participants, regardless of titration, stop of study medication, or rescue.

### 10.3. Statistical Analyses

#### 10.3.1. General Statistical Considerations

Statistical analysis of this study will be the responsibility of Lilly or its designee. Any change to the statistical methods described in the protocol will require an amendment only if it changes a principal feature of the protocol. Any other change to the statistical analyses and the justification for the change will be described in the statistical analysis plan (SAP) and/or clinical study report. Additional exploratory analyses of the data may be performed as deemed appropriate. Analyses will be fully detailed in the SAP.

Statistical analyses (including the primary analysis) will be conducted on the efficacy analysis set population. Safety analyses will be performed on the full analysis set.

No adjustments for multiplicity will be performed.

All tests of treatment effects will be conducted at a two-sided alpha level of 0.1 and/or two-sided 90% confidence interval, unless otherwise stated.

The baseline value used for the analyses will be the last scheduled baseline value obtained for each study participant prior to randomization. ALT, AST, and GGT will be average of 3 assessments as baseline.

The analysis of the main secondary efficacy endpoint and possibly other Bayesian analyses may be computed using Fixed and Adaptive Clinical Trial Simulator software. Remaining summaries and analyses will be performed using the SAS System.

